2.5 Randomization and Blinding

Study treatment assignment will be unknown to the subjects, investigators, study centers, the sponsor, and any contract research organization affiliated with the study other than those authorized to access treatment assignment for regulatory safety reporting and submission processes, interactive voice recognition/interactive web response system (IVRS/IWRS) administration and drug supply management (see protocol section: Blinding of Study Treatments).

Cabozantinib-matched placebo will be packaged and color-, size-, and shape-matched to be indistinguishable (including imprint on capsules) from cabozantinib.

Randomization will be stratified by the following factor:

• RET M918T status (positive vs negative vs unknown)

The M918T-unknown stratum will contain at most 10% of the total number of enrolled subjects and will be limited to subjects who undergo a tumor biopsy for the purpose of enrolling in the

study but the sequencing analysis of the tumor sample for the RET or RAS mutation status fails, a replacement sample is not available, and an additional biopsy procedure is not feasible.

The randomization scheme employs a permuted block design to help ensure a 1:1 ratio of assignment to the cabozantinib 60 mg or 140 mg groups for the overall population as well as within each level of the stratification factor. Subjects are defined to be enrolled in the study if they are randomized.

2.6 Radiographic Tumor Assessment

Radiographic tumor measurements will be made at screening, 12 weeks after randomization, and every 12 weeks thereafter. This schedule is to continue irrespective of whether study treatment is given, interrupted, reduced or discontinued. Tumor assessments will continue (and scans submitted to the IRC) through the later of:

- 12 weeks after radiographic progression per RECIST 1.1 as determined by the investigator (i.e., one additional assessment after investigator-determined radiographic progression), or
- The date of the decision to discontinue study treatment (eg, for subjects treated beyond radiographic progression per RECIST 1.1)

However, these assessments are to be discontinued if subsequent systemic anti-cancer therapy, radiation therapy, or surgery affecting tumor lesion(s) is initiated prior to meeting these above criteria.

An IRC will evaluate all blinded scans per RECIST 1.1 for disease progression and objective response for the purpose of evaluating primary and secondary study endpoints. Subject management and treatment decisions will be based upon investigator evaluations of the scans. The roles, responsibilities, and details of the processes followed by the IRC are provided in the IRC charter.

3 ANALYSIS POPULATIONS

3.1 Intent to Treat

The Intent-To-Treat (ITT) population, defined as all randomized subjects, will be used for efficacy analyses, with analyses according to the randomized treatment assignment.

3.2 Safety Population

The Safety population comprises of all subjects who receive any amount of study treatment. Analyses based on the Safety population will be performed according to the actual treatment received.

3.3 Per Protocol Population

A Per Protocol population is not defined or planned for the study.

4 GENERAL CONVENTIONS

The statistical principles applied in the design and planned analyses of this study are consistent with International Council for Harmonisation (ICH) E9 guidelines (ICH 1998).

Continuous data will be summarized using descriptive statistics (number of observations, mean, standard deviation, median, 25th and 75th percentiles, minimum, and maximum). Frequencies and percentages will be used for summarizing categorical (discrete) data.

Confidence intervals (CIs) will be constructed at the 95% level unless otherwise specified. For binomial variables, estimates will be obtained by using the normal approximation methods or Clopper-Pearson's method unless specified otherwise.

A month is operationally defined to be 30.4375 days. Six months is operationally defined to be 183 days. A year is operationally defined to be 365.25 days.

Data summaries will be presented by treatment arm unless otherwise specified.

4.1 **Definition of Baseline**

In general, for efficacy endpoints the last observed measurement prior to or on the date of randomization will be considered as the baseline measurement. Per schedule of assessment biomarker samples were collected prior to the first dose date hence the baseline measurements will be with respect to the first dose date. For subjects who did not take any study treatment, any biomarker sample available prior to randomization will be considered as baseline observation.

For safety endpoints, the last observation on or before date of first dose of study treatment will be considered the baseline measurement unless otherwise specified. For assessments on the day of first dose, where time is not captured, a nominal pre-dose indicator, if available, will serve as sufficient evidence that the assessment occurred prior to first dose. If neither time nor nominal pre-dose indicators are available, such assessments will be assumed to have occurred prior to first dose of study treatment.

4.2 Definition of Study Day

For the purpose of efficacy data summary, Study Day 1 is defined as the date of randomization to study treatment. For visits (or events) that occur on or after randomization, study day is defined as (date of visit [event] – date of randomization + 1). For visits (or events) that occur prior to randomization, study day is defined as (date of visit [event] – date of randomization). There is no Study Day 0.

For the purpose of safety data summary, Dose Day 1 is defined as the date when the first dose of study treatment was received (referred to in the protocol as Week 1 Day 1). For visits (or events) that occur on or after first dose of study treatment, dose day is defined as (date of visit [event] – date of first dose of study treatment + 1). For visits (or events) that occur prior to first dose of study treatment, dose day is defined as (date of visit [event] – date of first dose of study treatment). There is no Dose Day 0.

For the derivation of "days since last dose of study treatment" (such as for adverse events [AEs]) this is defined as (event date – date of last dose of study treatment). Events that occur on the same day as the last dose of study treatment will therefore be described as occurring zero days from the last dose of study treatment.

4.3 Visit Window Calculation

The planned analyses do not require the calculation of visit windows except for tumor assessments as described in Section 7.1.3.

4.4 Missing and Partial Data

In general, other than for partial dates, missing data will not be imputed and will be treated as missing. The algorithms for imputation of partial dates vary depending upon the parameter. These are presented in Appendix A.

4.5 Safety Observation Period

The safety observation period is defined as time from first dose date of study treatment to the earliest of the date of the decision to permanently discontinue study treatment+ 30 days or date subject withdrew consent or date of death or data cut-off date.

Generally only the safety data (including adverse events, laboratory results, vital signs, ECG, ECOG PS, and concomitant medications) reported during the safety observation period will be analyzed and summarized, unless otherwise specified in this plan.

4.6 Definition of Prior, Concomitant, and Subsequent Therapy

For the purpose of inclusion in prior and/or concomitant medication tables, incomplete medication/therapy start and stop dates will be imputed as detailed in Appendix A. Based on imputed start and stop dates:

- Prior medications/radiation therapies are defined as medications with a start/stop date occurring before the date of first dose of study treatment.
- Concomitant medications/radiation therapies are defined as medications that stop or continue on or after date of first dose day through the end of safety observation period.
- Concomitant and Subsequent non-radiation anticancer therapies/radiation therapies are defined as those that stop or continue on or after the date of randomization.

Medications/radiation therapies may be summarized as prior, concomitant and/or subsequent.

4.7 Software

All analyses will be conducted using SAS Version 9.3 or higher.

4.8 Changes to Planned Analyses

Substantive changes to the analyses described in the protocol or in approved versions of this plan will be fully documented in a revised version of the plan approved by the Sponsor prior to conducting unblinded analyses.

Clarifications, minor corrections, and operational considerations necessary to accurately conduct the analyses that do not materially change the nature of the analysis will be documented in an addendum to this plan that will be also be approved by the Sponsor prior to unblinding the study to conduct the analyses.

4.9 Subject Data Listings

Full archival case report tabulations are not planned. Listings described in the ICH E3 guidance document-Structure and Content of Clinical Study Reports will be provided.

5 STUDY POPULATION SUMMARIES

5.1 Enrollment

Subjects are defined to be enrolled at randomization. Enrollment will be summarized by (a) country and study center and (b) geographic region, country and protocol version.

5.2 Disposition

Subject disposition will be summarized categorically and will include the number and percentage of subjects in the ITT and Safety Populations. The reasons for study treatment discontinuation and discontinuation from radiographic tumor assessment follow-up will also be summarized categorically.

5.3 Demographic and Baseline Characteristics

Summaries of demographics, stratification factors and baseline characteristics will be presented for subjects in the ITT and Safety populations.

A. The demographic characteristics consist of:

- Age (continuous) in years
- Age category 1 (<65 years,≥65 years)
- Age category 2 (<45 years, 45 to <65 years, 65 to <75 years, 75 to <85 years, ≥85 years)
- Age category 3 (<65 years, 65 to <75 years, 75 to <85 years, ≥85 years)
- Age category 4 (<75 years, ≥75 years)
- Sex (Male, Female)
- Ethnicity (Hispanic or Latino, Not Hispanic or Latino, Not Reported)
- Race (American Indian/Alaska Native, Asian, Black/African American, Multiple, Native Hawaiian or Other Pacific Islander, White, Not Reported, Other)
- Race category (White, Non-White, Not Reported)
- Geographic region (Europe, Rest of the World)

B. Categorical summaries of RET M918T mutation status

• The stratification factor-RET M918T status at randomization (positive vs negative vs unknown) will be presented as recorded (a) per IxRS and (b) per CRF.

C. Baseline characteristics include:

- Weight in kilogram (kg)
- Weight in kg category (< 60, >=60 to <=80, >80)
- Height in centimeters (cm)
- Body Mass Index (BMI) in kg/meter² is calculated as (weight (kg)*10000)/(Height (cm))²
- ECOG Performance Status (0, 1)
- Smoking status (Never, Former, Current, Missing)

5.4 Medical History

General medical history data will be coded per MedDRA.

5.5 Cancer History and Baseline Disease Status

Cancer history and current disease characteristics will be summarized categorically or with descriptive statistics as appropriate for all subjects in the ITT population and will include:

- Diagnosis of MTC by histology (Yes, No)
- Time in years to randomization since initial diagnosis of MTC as identified by histology
- Time in years to randomization since initial metastasis
- Time in years to metastatic disease since initial diagnosis of MTC as identified by histology
- Cancer stage per investigator (TNM Stage I, II, III, IV [A, B, C], Unknown)
- Primary tumor per investigator (T0, T1[A, B], T2, T3, T4 [A,B])
- Regional lymph nodes per investigator (NX, N0, N1 [a, b])
- Distant metastasis per investigator (M0, M1)
- Extent of metastatic disease at current diagnosis (a) per IRC and (b) per investigator
- Number of target and non-target lesion locations at screening (0, 1, ≥ 2) (a) per IRC and (b) per investigator
- Has brain metastasis at baseline as identified on the target or non-target lesion CRFs (Yes, No)
- Time in months from historical reference scan to the date of qualifying scans

- Receipt of prior non-radiation anti-cancer agents, radiation therapy, or surgery/procedure for MTC (Yes, No)
- Serum Calcitonin (pmol/L) descriptive summary
- Carcinoembryonic antigen (CEA) (ug/L) descriptive summary

Incomplete diagnosis dates will be imputed as detailed in Appendix A.

6 TREATMENTS, MEDICATIONS, SURGERIES/PROCEDURES

Please refer to Section 4.6 for definitions of prior and concomitant therapies.

6.1 Prior Non-Radiation Anti-Cancer Therapy

Prior non-radiation anti-cancer therapies will be coded per World Health Organization drug dictionary (WHO-DD).

The following will be summarized categorically or with descriptive statistics as appropriate for all subjects in the ITT and Safety population:

- Subjects with receipt of prior non-radiation anti-cancer and radionuclide agents by indication and therapy type
- Number of prior non-radiation anti-cancer agents and radionuclides received per subject for MTC
- Number of prior systemic non-radiation anti-cancer agents and radionuclides received per subject for MTC
- Reason for stopping the most recent prior systemic non-radiation anti-cancer/radionuclide agent received by subject for MTC (progressive disease, toxicity, other)
- Time in months to randomization since latest reported prior systemic non-radiation anticancer/radionuclide agent for MTC

All prior non-radiation anti-cancer agents will be summarized categorically by Anatomical Therapeutic Chemical (ATC) Class Text and WHO-DD base substance preferred name by treatment arm and type of therapy (Systemic, Local, Other, Unknown) for all subjects in the ITT and Safety populations.

Subjects will also be grouped into one or more of the following categories based on the systemic therapy received:

- Cytotoxic agents
- Multi tyrosine kinase inhibitors (TKI) (without RET inhibitor activity)
- o Multi tyrosine kinase inhibitors (TKI) (with RET inhibitor activity)
- RET-specific inhibitors
- Immunotherapy (PD-1/PD-L1/CTLA4/Other)
- Other systemic therapies

6.2 Prior Radiation Therapy

For all subjects in the ITT population summarization of prior radiation therapy will include:

- Receipt of prior radiation therapy (Yes, No) by indication
- Number of prior radiation therapy received per subject for MTC
- Descriptive statistics for time in months to randomization since latest reported radiation therapy for MTC

6.3 Prior and Concomitant Medications (Excluding Anti-cancer Therapy)

Medications recorded on the CRFs will be coded using the WHO-DD. Prior and concomitant medications, other than prior and subsequent anti-cancer therapies, will be summarized by treatment arm for all subjects in the Safety and ITT populations by ATC and WHO-DD base substance preferred name. Concomitant and subsequent anti-cancer therapies are addressed in Sections 6.8 and 6.9 of this plan.

6.4 Prior Surgeries/Procedures

For all subjects in the ITT population summarization of prior surgeries and procedures will include:

- Receipt of prior surgery/procedure (Yes, No) by indication
- Number of subjects who received prior surgery/procedure related to MTC
 - o Number of subjects who received partial thyroidectomy only
 - o Number of subjects who received total thyroidectomy only
- Descriptive statistics for time in months to randomization since latest reported thyroidectomy

6.5 Study Treatment Exposure

Study treatment exposure will be summarized for all subjects in Safety population.

The following will be derived for each subject and descriptive summaries will be provided:

- Duration of exposure including dose holds in months, calculated as (date of decision to discontinue study treatment date of first dose of study treatment + 1) / 30.4375
- Average daily dose per subject (mg/day) of cabozantinib, calculated as (total dose received/duration of exposure)
- Percent dose intensity for cabozantinib calculated as 100*(average daily dose received mg/day)/(planned dose mg/day), where planned dose is either 140 mg/day or 60 mg/day.
- Duration of exposure excluding dose holds in months, calculated as [(date of decision to discontinue study treatment date of first dose of study treatment + 1)-(sum of all dose holds)] / 30.4375

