## 1.4.3.2.1 Safety Results for the Phase 3 Study XL184-301

As of 31 December 2011, the median duration of exposure was 315 days (10.35 months) in cabozantinib-treated subjects and 104.0 days (3.4 months) in placebo-treated subjects. Twenty-five percent of subjects in the cabozantinib arm had a duration of exposure of 468 days or more compared with 197 days or more in the placebo arm.

The 140 mg dose regimen included 2 levels of dose reduction to manage toxicities (100 mg [first level] and 60 mg [second level]). As of 31 December 2011, 81% of cabozantinib-treated subjects underwent at least a first-level dose reduction to 100 mg and 44% underwent a second-level dose reduction to 60 mg. In comparison, 11% of placebo-treated subjects had a first-level dose reduction, and 0.9% had a second-level dose reduction. Sixty-nine percent of cabozantinib-treated subjects had a dose delay due to an AE compared with 17.4% of placebo-treated subjects. The median duration of these dose delays was 4.0 days and 8.0 days in cabozantinib-treated and placebo-treated subjects, respectively.

As a result of protocol-specified dose reductions, subjects' final recorded dose levels as of discontinuation or the data cut-off were distributed over the three protocol-permitted dose levels (140, 100, and 60 mg qd; 175, 125, and 75 mg as the *S*-malate salt, respectively), There was a wide range of duration of exposure at all dose levels including at the 140 mg dose (Table 1-4).

Table 1-4: XL184-301: Duration of Exposure in Days for Subjects for Whom the Last Dose was 140 mg, 100 mg, 60 mg (Safety Population)

	Cabozantinib (N=214)	Placebo (N=109)
140 mg		
N	54 (25.2%)	98 (89.9%)
Median	178.5	103.0
Min, Max	8, 673	11, 823
100 mg		
N	71 (33.2%)	10 (9.2%)
Median	307.0	153.5
Min, Max	15, 843	15, 514
60 mg		
N	89 (41.6%)	1 (0.9%)
Median	347.0	356.0
Min, Max	37, 1077	356, 356

Doses are shown in freebase equivalent (FBE) weight.

Note: One subject in the cabozantinib group had a last dose level of 100 mg which was not protocol specified.

Duration of exposure: date of last dose - date of first dose + 1

Source: XL184-301 Safety Addendum, Table 14.3.1.23

The six most frequently reported AEs in Study XL184-301 were diarrhea (66.8% cabozantinib, 35.8% placebo), weight decreased (54.2%, 11.0%), PPE (51.4%, 1.8%), decreased appetite (48.6%, 15.6%), nausea (44.9%, 21.1%), and fatigue (41.6%, 30.3%).

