		earlier of 12 weeks after radiographic PD per RECIST 1.1 per		
		Investigator or the date of initiation of subsequent systemic anti-		
		cancer therapy.		
		The sample size of the study may be increased to up to 250		
		subjects if a review of the accumulating PFS events suggests		
		that the number required for the event-driven primary analysis		
		will not be reached (due to censoring) among the approximately		
		188 subjects originally enrolled.		

Table 2: SAP Version History

Date	Version	Primary Reason(s) for Amendment	
2014 Sep 26	V1.0	Not Applicable	
2020 Jun 02	V2.0	Implemented Protocol Amendment 4 changes	
		All efficacy analyses will be presented w.r.t stratification factors based on IxRS and CRF	
		Per protocol population deleted as analyses by ITT population is deemed more robust	
		Baseline biomarkers defined w.r.t first dose date as samples were collected prior to first dose date and not prior to randomization (Section 4.1)	
		Added a section for defining safety observation period (Section 4.5)	
		Refined summaries for demographic and baseline characteristics to remove baseline laboratory characteristics (Section 5.3)	
		Refined summaries for cancer history and disease status to include cancer staging, calcitonin, and CEA (Section 5.5)	
		Refined summaries for treatments, medications, surgeries/procedures to include systemic therapy by special categories, prior radiation therapy, and prior surgeries/procedures (Section 6)	
		Exposure summary will be in months instead of weeks	

Date	Version	Primary Reason(s) for Amendment		
		(Section 6.5)		
		Added PFS per IRC analysis time computation in months (Section 7.1.1)		
		Updated censoring rules for analysis of PFS to include censoring due to radiation (other than to bone) and surgery to soft tissue. Also added additional PFS censoring rules per EMA. (Table 3)		
		Added clarification to the definition of ORR (Section 7.2.1)		
		Subgroup categories refined to include receipt and number of prior systemic non-radiation anti-cancer therapy due to MTC, and to remove receipt of prior Vandetanib (Section 7.6)		
		Refined AE summaries in Table 4		
		Added sponsor-defined grades for LDH (Section 8.5.1)		
		Added summaries for liver function abnormalities and renal failure screening criteria, and updated eGFR calculated (Section 8.5.2)		
		Added clarification to include all QTcF measurements at a time point if more than 3 measurements are done (Section 8.8)		

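### SAP 6.5 labels average daily dose mg/day but divides by a duration defined in months, and does not say which of its two durations applies (minor)

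*SAP*

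**What the plan says.** SAP 6.5 lists four derived exposure items for the Safety population, in this order:

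1. "Duration of exposure including dose holds in months, calculated as" the span from first dose to the decision to stop, counted inclusively, over 30.4375.
2. "Average daily dose per subject (mg/day) of cabozantinib, calculated as (total dose received/duration of exposure", with the bracket closed there.
3. Percent dose intensity, "100*(average daily dose received mg/day)/(planned dose mg/day" with the bracket closed, "where planned dose is either 140 mg/day or 60 mg/day".
4. "Duration of exposure excluding dose holds in months, calculated as" the same span less the sum of all holds, over 30.4375.

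SAP 4 supplies the conversion: "A month is operationally defined to be 30.4375 days". No other SAP section gives an exposure duration in days for use in item 2. Both durations end at the decision to discontinue; SAP 6.5 gives no end date for a subject still being treated at the cut-off.

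**The concern.** The units do not agree. Milligrams divided by months gives mg per month, yet the result is labelled mg/day and then set against a planned dose in mg/day. The denominator is also not identified: item 2 refers to duration of exposure without saying whether hold days count.

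The second gap is the one that could reach a table unnoticed, because either choice gives a believable percentage. If hold days are left out, interruptions no longer lower dose intensity. Dose modification frequency is a listed endpoint, and Protocol 1.5.1 expects fewer reductions and interruptions at the lower starting dose. A measure that ignores interruptions would hide part of that difference between arms.

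**Working it through.** **Inputs**

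- 30.4375 days per month (SAP 4 and 6.5).
- Planned doses of 60 and 140 mg/day (SAP 6.5).
- 315 days of exposure, for illustration only. Protocol 1.4.3.2.1 reports for the cabozantinib arm of the earlier Phase 3 study that "the median duration of exposure was 315 days (10.35 months", with the bracket closed.
- Total days held: assumed, since the documents give no totals for this trial. I use 4 and 65 (the median and the maximum length of a delay in the earlier study, Protocol synopsis, Rationale), 42 (the six weeks allowed per interruption, Protocol 6.5.1) and 28 as an intermediate value.

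**Conversion check.** SAP 6.5 states no numerical result to reproduce. The conversion agrees with the protocol's own figure: 315 / 30.4375 = 10.349, reported as 10.35 months.

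**Unit check: 315 days, no holds or reductions**

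| Arm | Total dose (mg) | Literal: total / (315 / 30.4375) | In days: total / 315 | Intensity, literal | Intensity, days |
|---|---|---|---|---|---|
| 60 mg | 60 × 315 = 18,900 | 1,826.25 | 60.0 | 3,043.75% | 100% |
| 140 mg | 140 × 315 = 44,100 | 4,261.25 | 140.0 | 3,043.75% | 100% |

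The ratio is 30.4375 for every subject, whichever duration is used, because both durations carry the same divisor.

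**Choice of duration: in days, full dose whenever dosed**

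With H days held, total dose = planned dose × (315 − H). Intensity is 100 × (315 − H) / 315 with holds counted and 100 × (315 − H) / (315 − H) = 100% without. The planned dose cancels, so the result is the same in either arm.

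| Days held | Holds counted | Holds excluded |
|---|---|---|
| 4 | 98.7% | 100% |
| 28 | 91.1% | 100% |
| 42 | 86.7% | 100% |
| 65 | 79.4% | 100% |

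**With reductions, 140 mg arm (assumed course):** 44 days at 140 mg, 28 days held and 243 days at 60 mg. Total = 6,160 + 14,580 = 20,740 mg. With holds counted, 20,740 / 315 = 65.8 mg/day, or 47.0%. Without, 20,740 / 287 = 72.3 mg/day, or 51.6%.

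**The case against.** **The intended unit is plain.** The mg/day label appears on the average dose, again inside the intensity formula, and on the planned dose. A programmer has to work in days to satisfy those labels, and an intensity near 3,000% would be noticed. This stands. A reader might infer that the reported exposure tables will be wrong 30-fold; the documents do not support that. The formula is wrong as written, but the error is unlikely to survive programming.

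**The order of the bullets points to counting holds.** When average daily dose is introduced, only the duration that includes holds has been defined. This also stands as the more natural reading, although the text does not state it. A reader might infer that the plan will overstate the dose delivered in the 140 mg arm, but nothing in the SAP says that holds are excluded.

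**Typical hold time may be short.** The earlier study reports a median of 1.5 delays and a median delay of 4.0 days. Medians do not multiply, but as a rough guide 6 days in 315 gives 98.1% against 100%. The upper end of the range above should not be taken as typical.

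**Other summaries show delivered dose.** SAP 6.6 already tabulates, by arm, time at each dose level including 0 mg, lowest and last dose level, and AE-related holds and their lengths; SAP 6.7 counts subjects with holds for other reasons. So it goes too far to say that this figure is needed to interpret a non-inferior PFS.

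**The version history does not show when the mismatch arose.** It records that "Exposure summary will be in months instead of weeks". It would be tempting to conclude that V2.0 introduced the error. The V1.0 dose formula is not in the documents, and its exposure unit was weeks, not days, so that inference is unsupported.

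**The SAP uses a cut-off nearby.** The safety observation period (SAP 4.5) can end at the data cut-off, and Appendix A uses the cut-off when imputing incomplete dosing stop dates. These show how the gap for ongoing subjects could be filled, but neither changes the SAP 6.5 formula.

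**Conclusion.** The point holds, at minor severity. As written, SAP 6.5 returns mg per month under a mg/day label, and percent dose intensity carries the same factor of 30.4375. That factor follows from the text alone and needs no assumption.

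The unnamed duration is a separate ambiguity. Its size depends on hold time: 1.3 to 20.6 percentage points for 4 to 65 days held, assuming 315 days of exposure at full dose when dosed (100 − 98.7 and 100 − 79.4). The missing end date for subjects still on treatment is a real but small gap.

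All of this concerns descriptive Safety-population summaries. The PFS and ORR analyses and the control of type I error do not use average daily dose or dose intensity.

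**What to change.** In SAP 6.5, write:

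- Average daily dose (mg/day) = total mg received / duration of exposure in days, with dose holds counted.
- Percent dose intensity = 100 × that value / planned dose (140 or 60 mg/day).
- For subjects still on treatment, the duration ends at the data cut-off date.
- Months are used only when the two durations themselves are summarised.

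The cost is a few lines of wording and a check of the exposure program; no new data are needed. SAP 4.8 provides the route: a revised SAP, or an addendum for minor corrections approved by the sponsor before unblinding.
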